Period	The subdivisions of the trial design (e.g. Screening, Treatment, Follow-up) which are described in the Protocol. Periods define the study phases and will be used in clinical trial database setup and eventually in analysis
Perpetrator drug	A drug which affects the pharmacokinetics of the other drug
Personal data	Participant information collected by the Investigator that is coded and transferred to Novartis for the purpose of the clinical trial. This data includes participant identifier information, study information and biological samples
Premature participant withdrawal	Point/time when the participant exits from the study prior to the planned completion of all study drug administration and/or assessments; at this time all study drug administration is discontinued, and no further assessments are planned
Randomization number	A unique identifier assigned to each randomized participant
Run-in Failure	A participant who is screened but not randomized/treated after the run-in period (where run-in period requires adjustment to participant's intervention or other treatment)
Screen Failure	A participant who did not meet one or more criteria that were required for participation in the study
Source Data/Document	Source data refers to the initial record, document, or primary location from where data comes. The data source can be a database, a dataset, a spreadsheet or even hard-coded data, such as paper or eSource
Stage in cancer	The extent of a cancer in the body. Staging is usually based on the size of the tumor, whether lymph nodes contain cancer, and whether the cancer has spread from the original site to other parts of the body
Start of the clinical trial	The start of the clinical trial is defined as the signature of the informed consent by the first participant
Study treatment	Any drug or combination of drugs or intervention administered to the study participants as part of the required study procedures; includes investigational drug(s), control(s) or background therapy

Study treatment discontinuation	When the participant permanently stops taking any of the study drug(s) prior to the defined study treatment completion date (if any) for any reason; may or may not also be the point/time of study discontinuation
Tele-visit	Procedures or communications conducted using technology such as telephone or videoconference, whereby the participant is not at the investigative site where the investigator will conduct the trial

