2.2 Secondary estimands

Not applicable.

3 Study design

This study is an open-label, multi-center, prospective eighteen-month study in a minimum of

118 MS patients with early RRMS (defined as within 6 months of diagnosis of clinically

definite RRMS) and who are disease modifying therapy (DMT) treatment naïve. RRMS patients will be benchmarked against age- and sex-matched healthy controls (n=50) for select secondary [REDACTED]. A screening period of 4 weeks will be used to assess eligibility and the assessment to address the primary objective will be performed at the end of the maintenance period (Month 18). There will be one interim analysis after the last participant completes his/her Month 18 (primary analysis time point) visit. Participants who complete the treatment period or who prematurely discontinue study drug and the study, and do not continue on any MS DMT, will undergo a safety evaluation 100 days following last dose of study treatment (captured only in source documents and only for ofatumumab treated participants), and will be discharged from the study if they choose to not be included in the optional extension portion of the trial for an additional 12 months (up to 30 months total in trial). Healthy control participants will not have a safety evaluation post end of study. Additional efficacy and safety assessments will be evaluated during the optional open-label extension to further elucidate the long-term clinical and radiological effects of ofatumumab (Figure 3-1). Of note, MRI data will be re-baselined at month 6 to account for treatment-related pseudo atrophy.

[figure not shown]
Eligible participants with RRMS will receive ofatumumab 20mg subcutaneous doses at Baseline/Week 0 (Day 1), followed by Week 1 (Day 7), Week 2 (Day 14) and then every month thereafter, beginning at Week 4 (Month 1) until Month 18 (see Figure 3-1). Additional efficacy and safety assessments will be evaluated up to 30 months, necessitating ofatumumab monotherapy over the course of up to 30 months. Ofatumumab will be administered according to the United States Prescribing Information (USPI). RRMS patients must remain on ofatumumab monotherapy to remain in the trial, with no DMT switching or combination DMT therapy allowed. Healthy controls will not be given a therapy.

Assessments will be performed per the assessment schedule found in Table 8-1.

Figure 3-1 Study design

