4.2 Rationale for dose/regimen and duration of treatment

Ofatumumab dose

The dose regimen for ofatumumab, for this study is an initial dose regimen of 20mg at Baseline/Week 0 (Day 1), followed by Week 1 (Day 7), Week 2 (Day 14) and every month thereafter, beginning at Week 4 (Month 1), until Month 18 (see [Figure 3-1](#)).

This dosing regimen is consistent with the dose and regimen in the Phase 3 development program of ofatumumab in RMS and in the US prescribing information.

Duration of treatment

Treatment duration within the primary study will be 18 months. RRMS patients must remain on ofatumumab monotherapy to remain in trial, with no DMT switching or combination therapy allowed. Additional efficacy and safety assessments will be evaluated during an optional 12-month open-label extension necessitating ofatumumab monotherapy over the course of up to 30 months (see [Figure 3-1](#)).

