Participants who discontinue study treatment or who decide they do not wish to participate in the study further should NOT be considered withdrawn from the study UNLESS they withdraw their consent (see [Section 9.2](#)). Where possible, they should return for the assessments indicated in the visit assessment schedule ([Table 8-1](#)). If they fail to return for these assessments for unknown reasons, every effort (e.g. telephone, e-mail, certified letter) should be made to contact the participant/pre-designated contact as specified in the 'Lost to Follow-up' [Section 9.1.3](#). This contact should preferably be done according to the study visit assessment schedule.

If the participant cannot or is unwilling to attend any visit(s), and has not withdrawn consent to participate, the site staff should maintain regular telephone contact with the participant, or with a person pre-designated by the participant. This telephone contact should preferably be done according to the study assessment schedule.

After discontinuation from study treatment, at a minimum, in abbreviated visits, the following data should be collected at clinic visits or via telephone/email contact:

- New / concomitant treatments
- Adverse Events / Serious Adverse Events

The investigator must also contact the IRT to register the participant's discontinuation from study treatment.

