## 2 Statistical methods

### 2.1 Data analysis general information

The statistical analysis outlined in this SAP will be performed by United BioSource LLC (UBC), a Novartis-designated Contract Research Organization (CRO), using SAS® version 9.4 or higher.

The primary analysis will be based on Month 18 data, i.e., all data up to and including Month 18. This analysis will be performed after all participants have completed their Month 18 visit, discontinued study treatment prior to Month 18 (ofatumumab-treated participants) or discontinued the study prior to Month 18 (healthy control participants) (see [Section 2.1.1](#) and [Section 2.13](#) for additional details). The final analysis will include all data through Month 30.

For continuous variables, descriptive statistics will include number of participants (n) with available data, mean, standard deviation, minimum, maximum, median and 25th and 75th percentiles. For categorical variables, frequency counts and percentages will be reported. Where appropriate, 2-sided 95% confidence intervals (CIs) for point estimates of the mean or proportion will be provided.

In general, data summaries will be presented for ofatumumab-treated participants in the relevant analysis set. In instances where data are collected for both ofatumumab-treated participants and healthy control participants, data summaries will be presented **by Cohort** (ofatumumab-treated participants or healthy control participants) and on all participants in the respective analysis set.

All data (collected or derived) will be listed appropriately.

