### 5.1.3.3 Other imputations

#### Non-response imputation

NRI assumes that a participant is a non-responder (treatment failure) if the participant does not have a complete set of valid response assessments (relapse, disability [EDSS] and MRI) in Months 6 to 18 after receiving at least one dose of ofatumumab. Hence, for missing data the primary endpoint of NEDA-3 in Months 6 to 18 (yes/no) will be imputed as “No”.

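### Protocol and SAP conflict on whether a participant who stops ofatumumab stays in the trial, so whether relapse, EDSS and MRI are observed after stopping can vary by site

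*Protocol*

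**What the plan says.** Protocol Section 3 states "RRMS patients must remain on ofatumumab monotherapy to remain in the trial", and SAP 1.1 repeats this. Protocol 4.2 states "RRMS patients must remain on ofatumumab monotherapy to remain in trial, with no DMT switching or combination therapy allowed". Section 6.1.4 is similar.

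Protocol 9.1.1 says that participants who discontinue study treatment "should NOT be considered withdrawn from the study UNLESS they withdraw their consent", and continues "Where possible, they should return for the assessments indicated in the visit assessment schedule". It then sets a floor: "After discontinuation from study treatment, at a minimum, in abbreviated visits, the following data should be collected at clinic visits or via telephone/email contact". The list that follows has two items, new or concomitant treatments and AEs/SAEs. Relapse, EDSS and MRI are not on it. The glossary says of stopping treatment that it "may or may not also be the point/time of study discontinuation".

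Three SAP rules use what is observed up to Month 18:

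- **Primary (mFAS; SAP 2.2, 2.5.3).** Participants who stop before Month 18 for reasons other than lack of efficacy or death are excluded unless they show disease activity. If they do, they count as non-responders. The exception is not limited to time on drug.
- **Observed case (SAP 2.5.6).** Membership requires the Month 6 and Month 18 visits.
- **NRI (SAP 5.1.3.3).** A participant counts as a failure if he or she "does not have a complete set of valid response assessments (relapse, disability [EDSS] and MRI) in Months 6 to 18".

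On timing, SAP 2.1 and 2.1.1 allow the primary analysis once each treated participant has completed Month 18 or "discontinued study treatment prior to Month 18 (ofatumumab-treated participants"). SAP Table 2, which sets the data cut-off, refers instead to discontinuing the study.

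**The concern.** Read literally, Sections 3 and 4.2 let a site end participation when ofatumumab stops, while 9.1.1 tells it to keep the participant and continue the schedule where possible. No passage ranks the two. Even a site that follows 9.1.1 can meet its stated minimum by telephone without collecting any NEDA-3 component.

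Take a participant who stops at Month 9 for an adverse event with no activity so far. Discharged, this person is outside the mFAS and a failure under NRI. Followed to Month 18 with complete data and no activity, the same person is a success under NRI and in the observed-case set. Followed and found active, the person enters the mFAS as a failure. The reported proportions would then partly reflect retention practice. NRI and observed case are the two supplementary analyses that vary the handling of missing data, no sensitivity analysis is planned (SAP 2.5.5), and both share this dependence.

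**Working it through.** **Inputs from the documents.** 118 enrolled, 100 evaluable, 15% drop-out, anticipated NEDA-3 of 80% or 85% (Protocol 12.8.1, SAP 3.1). Classification rules are from SAP 2.2, 2.5.3, 2.5.6 and 5.1.3.3. SAP Tables 3 and 6 give EDSS and MRI windows at Months 6, 12 and 18.

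**The plan's own figures.** 1.96 × √(0.80 × 0.20/100) = 7.84 points; 1.96 × √(0.85 × 0.15/100) = 7.00 points; 100/0.85 = 117.6, rounded up to 118. All reproduce.

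**Classification of one stopper** (reason other than lack of efficacy or death, activity-free at stopping):

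| Analysis | Discharged | Followed, later active | Followed, activity-free, complete data |
|---|---|---|---|
| Primary mFAS | excluded | failure | excluded |
| NRI | failure | failure | success |
| Observed case | excluded | failure | success |

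Follow-up after stopping can only add failures to the mFAS and can only add successes to NRI, so the two move in opposite directions.

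**Assumptions for the size.** There are 118 − 100 = 18 stoppers, all for other reasons and all activity-free when they stop. They are either all discharged or all followed with complete data. 80 of the 100 completers achieve NEDA-3. A fraction p of stoppers stays activity-free to Month 18. The documents give no value for p; 0.6 to 0.8 is assumed.

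- All discharged: mFAS and observed case 80/100 = 80.0%; NRI 80/118 = 67.8%.
- All followed: mFAS = 80/(100 + 18(1 − p)); NRI and observed case = (80 + 18p)/118.
- p = 0.8: mFAS 80/103.6 = 77.2%; NRI and observed case 94.4/118 = 80.0%.
- p = 0.6: mFAS 80/107.2 = 74.6%; NRI and observed case 90.8/118 = 76.9%.

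**Wider range, in whole participants, all followed:**

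| Active after stopping | mFAS | NRI and observed case |
|---|---|---|
| 0 of 18 | 80/100 = 80.0% | 98/118 = 83.1% |
| 4 of 18 | 80/104 = 76.9% | 94/118 = 79.7% |
| 9 of 18 | 80/109 = 73.4% | 89/118 = 75.4% |
| 18 of 18 | 80/118 = 67.8% | 80/118 = 67.8% |

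With 85 of 100 completers responding, all discharged gives mFAS 85.0% and NRI 72.0%. All followed with 4 of 18 active gives 85/104 = 81.7% and 99/118 = 83.9%.

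**If only half of the 18 could be retained** (also an assumption): mFAS 80/101.8 = 78.6% (p = 0.8) to 80/103.6 = 77.2% (p = 0.6); NRI 87.2/118 = 73.9% to 85.4/118 = 72.4%. The shifts are then about 1.4 to 2.8 points for the mFAS and 4.6 to 6.1 points for NRI.

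**The case against.** Section 9.1.1 is the operative section on stopping treatment, and it favours retention. The sentences in Sections 3 and 4.2 go on to bar DMT switching and can be read as a monotherapy rule rather than an instruction to discharge. The Protocol elsewhere treats stopping drug and leaving the study as separate events (glossary, Sections 8 and 9.1.2). The two-item minimum is a floor for abbreviated visits and remote contact, below the scheduled assessments requested first. All of this is fair. A reader might infer that a discharging site and a retaining site comply equally well; that is too strong, since discharging a consenting participant departs from 9.1.1. What stands is that the main clause in three places ties trial participation to staying on drug, and nothing says that 9.1.1 prevails.

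A reader might also infer that the damage cannot be repaired at analysis. For the mFAS this does not hold. Stoppers for other reasons who stay activity-free are excluded under either reading, and those who stop for lack of efficacy or death are non-responders under either reading. Only post-discontinuation activity matters, and a SAP rule could settle how it counts. For NRI and observed case, assessments never made cannot be recovered, but both are supplementary.

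The size is also open to challenge. Drop-outs include people who withdraw consent or are lost and cannot be retained under either reading, and real sites would be mixed. The study is single-arm and descriptive, with no hypothesis test (SAP 5.4). These points stand and limit the severity.

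**Conclusion.** The conflict is real and stands in current text. It can change which participants have relapse, EDSS and MRI data after stopping. The direct effect is on NRI and observed case; the primary mFAS estimate is affected only through activity seen after stopping, and only downwards.

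Under the all-or-none assumptions above, the primary estimate moves by about 3 to 5 points, inside the planned half-width of 7.8 points. NRI moves by about 9 to 12 points, outside it. These are outer bounds resting on an assumed off-drug activity rate, not forecasts, and the documents do not show what sites did. A reader might take the figures as evidence that the primary result is unreliable; the documents do not support that.

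The SAP inconsistency is confined to the timing sentence in 2.1 and 2.1.1. Table 2 already uses study discontinuation. Severity: should be fixed.

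**What to change.** 1. **Protocol 3, 4.2 and 6.1.4, and SAP 1.1, against Protocol 9.1.1.** Reconcile these for data collection only. One rule should state whether participants who stop ofatumumab without withdrawing consent continue the Month 6, 12 and 18 relapse, EDSS and MRI assessments that 9.1.1 already requests where possible. List them as expected data at attended visits where clinically appropriate, since the required stop reasons in 9.1.1 include pregnancy and PML. Keep the telephone/email minimum as the floor; MRI and EDSS should not be added to a minimum that is meant to be met remotely.
2. **SAP 2.2 and 2.5.3.** State one symmetric rule for data after discontinuation for reasons other than lack of efficacy or death. Either activity after stopping does not bring a participant back into the mFAS, or participants followed with complete data count whether active or activity-free. Retaining stoppers under the present one-sided rule would only add failures.
3. **SAP 2.1 and 2.1.1.** Align the timing sentence with Table 2, so that the analysis waits for treated participants who stopped drug but remain in the study.

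The cost is wording in both documents and, if retention is the rule chosen, a few more off-treatment visits at sites that now discharge. No rule on when treatment stops or on later therapy needs to change.

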9.1.2 Discontinuation from study

Discontinuation from study is when the participant permanently stops receiving the study treatment, and further protocol-required assessments or follow-up, for any reason.

If the participant agrees, a final evaluation at the time of the participant's study discontinuation should be made as detailed in the assessment table (refer to [Section 8](#)).

Discontinued patients will not be replaced in this trial.

9.1.3 Lost to follow-up

For participants whose status is unclear because they fail to appear for study visits without stating an intention to discontinue from study treatment or discontinue from study or withdraw consent/oppose to the use of their data/biological samples, the investigator must show "due diligence" by documenting in the source documents steps taken to contact the participant, e.g.

dates of telephone calls, registered letters, etc. A participant should not be considered as lost to follow-up until due diligence has been completed or until the end of the study.

9.2 Withdrawal of informed consent/Opposition to use data/biological samples

Withdrawal of consent/opposition to use data/biological samples occurs when a participant:

- Explicitly requests to stop use of their biological samples and/or data (opposition to use participant's data and biological samples)

and

- No longer wishes to receive study treatment

and

- Does not want any further visits or assessments (including further study-related contacts)

This request should be in writing (depending on local regulations) and recorded in the source documentation.

In this situation, the investigator should make a reasonable effort (e.g. telephone, e-mail, letter) to understand the primary reason for the participant's decision to withdraw their consent/opposition to use data/biological samples and record this information.

Where consent to the use of Personal and Coded Data is not required in a certain country's legal framework, the participant therefore cannot withdraw consent. However, they still retain the right to object to the further collection or use of their Personal Data.

Study treatment must be discontinued, and no further assessments conducted, and the data that would have been collected at subsequent visits will be considered missing.

Further attempts to contact the participant are not allowed unless safety findings require communicating or follow-up.

If the participant agrees, a final evaluation at the time of the participant's withdrawal of consent/opposition to use data/biological samples should be made as detailed in the assessment schedule [Table 8-1](#).

Novartis will continue to retain and use all research results (data) that have already been collected for the study evaluation, including processing of biological samples that has already started at time of consent withdrawal/opposition. No new Personal Data (including biological samples) will be collected following withdrawal of consent/opposition.

9.3 Study completion and post-study treatment

Study completion is defined as when the last subject finishes their Study Completion or End of Study visit and any repeat assessments associated with this End of Study visit have been documented and followed-up appropriately by the Investigator, or in the event of an early study termination decision, the date of that decision.

Subject is considered to have completed the study when they fulfill the following criteria:

1. Subject has completed the study in its entirety according to the approved duration of the study

2. Subject is eligible for commercially available ofatumumab after completing the minimum duration of 18 months in the study
3. The subject has not stopped the study due to one or more of the following reasons:
 - Study discontinuation ([Section 9.1.1](#))
 - Withdrawal of informed consent ([Section 9.2](#))
 - Lost to follow-up ([Section 9.1.3](#))

End of Study (EOS) visit is mandatory for all subjects. The EOS visit is conducted at the end of the Open-label Treatment at Month 18 unless the patient continues into the extension period (as stipulated above). EOS will be done for all subjects. For subjects that complete the study, the next (and last) scheduled visit is the EOS visit and should align with the overall assessment schedule rhythm. Subjects who prematurely discontinue study treatment, and study participation, will have their EOS visit as soon as possible and continue into the Safety Follow-up for 100 days according to assessment schedule [Table 8-1](#). The Investigator must provide follow-up medical care for all subjects who are prematurely withdrawn from the study or must refer them for appropriate ongoing care.

At the end of the study, the study team will provide a plan on how subjects will have access to ongoing treatment. Furthermore, if the treatment's risk-benefit ratio has turned negative and/or Novartis discontinues the development of the study treatment due to lack of efficacy and/or safety reasons, then Novartis will work with the investigators to transition the subjects onto locally available treatment or alternative treatment.

9.4 Early study termination by the sponsor

The study can be terminated by Novartis at any time for any reason.

This may include reasons related to the benefit/risk assessment of participating in the study, practical reasons (including slow enrollment), or for regulatory or medical reasons.

In taking the decision to terminate, Novartis will always consider the participant welfare and safety. Should early termination be necessary, participants must be seen as soon as possible and treated as a prematurely withdrawn participant. The Investigator may be informed of additional procedures to be followed in order to ensure that adequate consideration is given to the protection of the participant's interests. The Investigator or Novartis depending on the local regulation will be responsible for informing IRBs/IECs of the early termination of the trial.

10 Safety monitoring, reporting and committees

